1.0 PURPOSE

Preliminary evaluation of the safety and effectiveness of Transcutaneous Magnetic Stimulation (TCMS) for the relief of low back pain.

2.0 OBJECTIVE

To perform a preliminary study of the feasibility, safety, and effectiveness of TCMS for the relief of low back pain.

3.0 HYPOTHESIS

TCMS treatment will lead to a clinically meaningful reduction in lower back pain associated with degenerative lumbo-sacral spine disease.

4.0 PRODUCT

Zygood TransCutaneous Magnetic Stimulator (TCMS)

7.0 DESIGN

Single-site, randomized, single -blind, placebo-controlled, trial

8.0 INTERVENTION

Subjects will identify the location of pain on their back. A member of the study team will note the location on a drawing. The TCMS device will be placed at the site the patient

identified. (Low back pain is defined as pain below the costal margin posteriorly, extending as low as the upper buttocks.)

With only a hospital gown intervening, the clinician will place the active or sham TCMS device on the area of pain, turn the device on, and adjust the amplitude upward from 0.24T in increments of 10%, approximately every 6-10 seconds, until the 1.2T setting is achieved or the subject reports discomfort. If the patient reports discomfort, the amplitude will be adjusted downward as necessary to maintain patient comfort.

Treatment group: TCMS device set to 1.2 Tesla will deliver a dose of 10 pulses per minute for 9 minutes (total 90 pulses). The first minute will be dedicated to adjusting the amplitude until maximum is achieved and/or the subject reports a sensation.

Placebo group: the sham TCMS device will remain on the area of pain for 10 minutes. The sham TCMS device is engineered so as to make the same sound at the same intervals as the active device. The same procedures will occur as those with the active device. The first minute will be dedicated to adjusting the “sham” amplitude. The remaining 9 minutes will be the treatment period.

9.0 ASSESSMENTS

9.1 Numeric Pain Rating Scale (NPRS):

0 to 10 numerical pain rating scale with equally spaced numerical intervals ranging from 0 representing “no pain” to 10 representing the “worst imaginable pain”

9.2 Baseline severity (Pain Diary):

Patient will document in a diary the severity of their pain on each day of the preceding week just prior to treatment.

9.3 Severity during treatment (immediate benefit):

At 5- and 10-minutes

9.4 Severity after treatment is completed (treatment durability):

1, 2, 4, 8, 12, 24, 48 and 72 hours post-treatment.

9.5 We will also follow-up with patients at 7and 30 days post-treatment,

Data collected at baseline, 7 day and 30 day follow-up:

Global Pain Scale (GPS)

Medication usage -Case Report Form

Non-drug treatment -Case Report Form
Functional Status (ADLs, Mobility, Employment)- Case Report Form

Patient satisfaction with treatment- Case Report Form

Presence of unwanted treatment effects, including paresthesia, irritation or discomfort, referred pain, and motor effects. – Case Report Form

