11.0 DEFINITION OF SUCCESS

Treatment success is a 30% reduction in mean baseline pain score on the 0 to 10 Numeric Pain Rating Scale (NPRS) that persists at least 1 hour and occurs at any time in the period from treatment through 48-hour follow-up.

Study success is at least 3 of 10 treatment patients meeting the criteria for treatment success and no serious adverse events reported in any subject related to active treatment.

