18.0 INCLUSION /EXCLUSION CRITERIA

18.1 INCLUSIONS

1. Age \geq 18 years of age
2. Prescription pharmacologic treatment is insufficient for treatment of pain
3. Pain duration of \geq 6 months
4. Pain limits physical activity

5. Pain occurs daily
6. Chronic low back pain, with or without leg pain, associated with MRI or other imaging study consistent with lumbo-sacral spine disease with or without nerve compression
7. Failed back surgery patients without metal implant
8. Pain intensity ≥ 5 at the time of enrollment and a self-reported pain score of ≥ 4 over the 7 preceding days.

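### Analgesic use is not scheduled to be recorded alongside the 1–72 hour pain ratings, so a fall that follows an extra dose counts as treatment success under Section 11.0

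*Combined protocol and SAP*

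**What the plan says.** Section 9.5 introduces its list with "Data collected at baseline, 7 day and 30 day follow-up", and the list includes "Medication usage -Case Report Form". The form's look-back period, and whether it asks for dates or clock times, are not given.

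Section 9.4 sets pain ratings at "1, 2, 4, 8, 12, 24, 48 and 72 hours post-treatment", and Section 9.3 adds ratings at 5 and 10 minutes. In the study schedule table under Section 26.0, the rows from 5 minutes to 72 hours carry marks only for the pain rating and adverse events. The column for additional endpoints is marked only on Day 1 and at days 7 and 30. Section 19.0 describes the 48-hour call as a reminder and mentions no medication question.

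Section 11.0 begins "Treatment success is a 30% reduction in mean baseline pain score" and requires that the reduction "persists at least 1 hour and occurs at any time in the period from treatment through 48-hour follow-up". It sets no condition on analgesic intake. It continues: "Study success is at least 3 of 10 treatment patients meeting the criteria for treatment success", together with a requirement about serious adverse events related to active treatment.

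Section 18.1 admits subjects for whom "Prescription pharmacologic treatment is insufficient for treatment of pain". Section 18.2 excludes significant opiate changes in the year before entry. No section limits analgesics after treatment, asks for them to be logged by time, or says how a rating after a dose is to be classified. Section 12.0 lists medication usage among the effectiveness analyses and describes the active-versus-sham comparison as unpowered.

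**The concern.** The success rule credits the best qualifying hour in a 48-hour window. A short-acting analgesic can produce the same pattern. The subjects have daily pain that their prescriptions do not adequately control, so doses beyond the usual pattern within the window are plausible, although the documents give no rate. When such a dose is followed by a qualifying fall, the plan as written attributes the fall to the device.

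Two results are exposed. The first is the study-success declaration, which counts active-arm subjects only, so randomization to sham gives it no protection. The second is the active-versus-sham comparison. With 10 subjects per arm, analgesic use need not balance, and imbalance could act in either direction: it could exaggerate an effect, or hide a real one if sham subjects take more. Dose times not collected alongside the ratings cannot be dependably reconstructed once the study is over.

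**Working it through.** **Figure in the plan.** There is no calculated figure to reproduce. Section 16.0 gives 10 + 10 = 20 subjects on the basis of an estimate, with no significance level, power or effect size. What can be computed is how the 3-of-10 rule behaves.

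**Comparing the sections.** The success window runs from treatment to 48 hours (Section 11.0). Scheduled medication records fall before it (baseline) and after it (days 7 and 30); none falls inside it (Section 9.5 and the schedule table). The entry criterion on opiate stability looks backward from enrollment and does not cover the window.

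**Which falls are exposed.** A fall seen at 5 or 10 minutes and still present at 1 hour leaves little room for a new analgesic to be its cause. Falls first seen later are exposed, and the rule credits them equally. From 2 hours on, the Section 9.4 ratings are 2, 4, 4, 12 and 24 hours apart, so a dose can easily fall between two ratings.

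**Illustrative arithmetic.** Every input below is an assumption; none is in the documents.

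- p0 = responder rate from all causes other than the device and extra analgesics: 10% or 15%.
- s = share of subjects taking extra analgesic in the window: 20% to 40%.
- r = share of those who then have a 30% fall lasting an hour: 30% to 50%.

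With an inert device, and analgesic-driven falls independent of other responses, the responder rate is p = p0 + (1 − p0) × s × r. The chance of meeting the efficacy part of the rule is P(X ≥ 3) with X ~ Binomial(10, p).

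The product s × r runs from 0.20 × 0.30 = 0.06 to 0.40 × 0.50 = 0.20.

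| p0 | s × r | p | P(at least 3 of 10) |
|---|---|---|---|
| 0.10 | 0 | 0.100 | 7.0% |
| 0.10 | 0.06 | 0.10 + 0.90 × 0.06 = 0.154 | 19.0% |
| 0.10 | 0.20 | 0.10 + 0.90 × 0.20 = 0.280 | 56.2% |
| 0.15 | 0 | 0.150 | 18.0% |
| 0.15 | 0.06 | 0.15 + 0.85 × 0.06 = 0.201 | 32.5% |
| 0.15 | 0.20 | 0.15 + 0.85 × 0.20 = 0.320 | 66.9% |

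**Sensitivity without a background rate.** Set p0 = 0 and let q be the share of subjects whose qualifying fall comes from an analgesic. P(at least 3 of 10) is then 1.2% at q = 0.05, 7.0% at 0.10, 18.0% at 0.15, 32.2% at 0.20 and 61.7% at 0.30. It passes 5% at q of about 0.087 and 50% at about 0.26. A modest share of analgesic-driven falls is therefore enough to matter under this rule.

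**The case against.** A reader might infer that analgesics in the window go wholly unrecorded and that their effect can never be separated out. The documents do not support that. A medication form is completed at day 7, after the window, and may ask about it in retrospect; its fields are not shown. Section 12.0 plans to look at medication usage, and the concurrent sham arm permits a group-level contrast. What stands against the plan is narrower. No dose timing is specified, recall a week later is a weak basis for placing a dose before or after a 2- or 4-hour rating, and a group summary does not classify individual responders.

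Other objections carry some weight:

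- Baseline is a 7-day diary with no washout described, so relief from habitual dosing is already in the comparator. Only intake beyond the usual pattern matters, and its frequency is unknown. Subjects whose prescriptions work poorly may also get less from an extra dose than the illustration assumes.
- The plan does not say how one hour's persistence is established. If two consecutive ratings are needed, many short dips would fail and the figures above would be too high.
- The 7% and 18% starting values come from the uncontrolled 3-of-10 rule itself, not from analgesics. Only the increase belongs to this point.
- The study is preliminary, and Section 16.0 uses it to judge whether further work is warranted. A false pass would lead to another study rather than to an efficacy claim.
- Making the exclusion of post-dose falls the only success definition would condition the endpoint on behaviour after randomization, which treatment may itself change. This objection stands in full, and the exclusion belongs in a sensitivity count.

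**Conclusion.** The point holds in limited form. No analgesic record is scheduled at the time of the ratings that decide treatment success, and Section 11.0 is silent on analgesics. A fall after an extra dose therefore counts for the device and toward 3 of 10, and cannot reliably be identified at subject level afterwards. Early falls that hold to 1 hour are largely outside the problem.

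The size of the bias cannot be derived from the documents. The increase from 7% to 19–56% (or from 18% to 32–67% on a 15% starting rate) depends wholly on the assumed rates of background response, extra use and relief, on independence, and on short falls meeting the persistence condition. The upper ends are the least favourable combinations of those assumptions. The figures show that the rule is sensitive; they do not estimate the false-success rate of this trial. The change should be made because it is cheap and the information is hard to recover later.

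**What to change.** 1. At each existing rating from treatment through 72 hours, ask for any pain medicine since the last rating, with name, dose and clock time. The schedule table's pain column already refers to the interval since the previous rating, so the item fits the same form.
2. Keep the Section 11.0 responder count as defined. Prespecify beside it, for both arms, the count that excludes falls first appearing after an analgesic beyond the usage recorded at baseline. Define in advance what that means for as-needed medicines, and how the one-hour persistence is read from the ratings.
3. State any claim of study success on both counts.

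This concerns recording and reporting only; treatment, sample size and the existing endpoint stay as they are. The cost is a short added item at each rating, slightly more burden on subjects, and possibly a less favourable second count.

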10.0 ADDITIONAL DATA COLLECTED

Demographic information (age, sex, ethnicity, employment status) and medical history and result of physical examination, including weight, height, pain diagnosis (noting any nerve compression), pain characteristics, pain etiology, pain duration, pain location (noting any leg pain), treatment history, and results of imaging study or studies.

11.0 DEFINITION OF SUCCESS

Treatment success is a 30% reduction in mean baseline pain score on the 0 to 10 Numeric Pain Rating Scale (NPRS) that persists at least 1 hour and occurs at any time in the period from treatment through 48-hour follow-up.

Study success is at least 3 of 10 treatment patients meeting the criteria for treatment success and no serious adverse events reported in any subject related to active treatment.

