17.0 RECRUITMENT, ENROLLMENT, AND ELIGIBILITY CONFIRMATION

All potential subjects identified through standard clinical practice at the site will be listed on a Screening Log and provided with detailed study information, including a description of TCMS.

We anticipate that 350 patients will be screened and 20 patients will be randomized to either placebo or intervention

If the subject is willing to participate, written informed consent will be obtained.

A subject is considered provisionally enrolled upon completion of the informed consent process.

Subjects provisionally enrolled will be taught how to complete a 7-day diary recording low back pain and will complete this diary before randomization (Self-Report).

Subjects will not be told the pain scores are needed for study inclusion.

The principal investigator or a member of the study team will review the diary to confirm that the subject's mean pain intensity score meets the inclusion criteria. Subjects who do not complete the diary or who fail to meet preliminary pain eligibility requirements will not be randomized, are ineligible for participation in the study and will not be counted in the number of enrolled patients. In such cases, the principal investigator or an authorized designee will log this into the data collection system.

If a patient is unable to tolerate at least 50% of the max 1.2T they will be excluded from the study.

** A significant change for this study is defined as a 20% increase or decrease in dosing of the patient's opioid dose and/or or a change in the medication class (adding or removing other types of medicine used to treat pain).*

*** This exclusion is restricted to opioids, benzodiazepines and psychotropics.*

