26.0 DATA ANALYSIS

Descriptive statistics, trend analysis of endpoint means for effectiveness. Tabular collection of adverse events with narrative

STUDY SCHEDULE AND DESCRIPTION OF DATA COLLECTION

Time of data collection	Data collected						
	Log entry	Demographics	History	Informed consent	NPRS first rating or since last rating given	AE	Additional endpoints
*Eligibility screened and offered participation	X	X	X	X			
*Pain each day in 7-day period					X	X	
Day 1 (baseline = start of treatment)					X	X	X
During treatment: 5 minutes					X	X	
10 minutes					X	X	
After treatment: 1 hour					X	X	
2 hours					X	X	
3 hours					X	X	
4 hours					X	X	
8 hours					X	X	
12 hours					X	X	
24 hours					X	X	
48 hours					X	X	
72 hours					X	X	
*Final assessment 7 & 30 days (+3)		X (employment status only)			X	X	X

*Data can be collected in person, via mail, via telephone, email, or fax

LAY SUMMARY

The study will evaluate whether an experimental medical device that emits a brief, intense magnetic field will relieve pain in the low back. The United States Food and Drug Administration (FDA) has approved a similar device for treatment of migraine, but this type of device has not been studied for the treatment of low back pain. No significant adverse reactions or side effects have been reported from the use of magnetic stimulation for headache treatment. Some patients who have migraine headaches have excellent pain relief with the magnetic treatment even if they did not get pain relief with medications.

We do not know whether magnetic treatment will relieve low back pain, so we will test this by applying a powerful electromagnet to the painful area of the low back. In some subjects, the magnet will be turned on, but in other patients the magnet will not be turned on. Neither subjects nor subjects' treating doctor will know whether the magnet was turned on or not, although the study team will know which subjects received treatment with magnetic pulses. The effect on pain will be recorded periodically for 2 days. If the subjects' reported pain is reduced as a result of the magnetic treatment compared with subjects who did not have the magnet turned on, then the magnet might have reduced the pain. Additional studies will be needed to further investigate whether this therapy reduces low back pain.

Keywords: **low back pain, TCMS (Transcutaneous Magnetic Stimulation), TENS (Transcutaneous Electrical Nerve Stimulation)**

RATIONALE AND BACKGROUND

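### Section 11 declares study success from active subjects alone: the same responder rule should be applied to sham and reported beside 3 of 10, and its baseline should be defined

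*Combined protocol and SAP*

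**What the plan says.** **Success rule (Section 11.0).** For an individual subject, the rule requires a "30% reduction in mean baseline pain score on the 0 to 10 Numeric Pain Rating Scale (NPRS) that persists at least 1 hour". Its timing condition is that this "occurs at any time in the period from treatment through 48-hour follow-up". The trial-level criterion is then "Study success is at least 3 of 10 treatment patients meeting the criteria for treatment success", together with no serious adverse event related to active treatment. The individual definition is not restricted to one arm. The trial-level count is.

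**Comparison with sham (Section 12.0).** A descriptive comparison of active and sham, unpowered by its own statement, is planned on change in NPRS and is labelled a cumulative responder analysis. The section gives no baseline, time window or persistence requirement for it.

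**Baseline.** Section 9.2 treats the diary as baseline severity: "Patient will document in a diary the severity of their pain on each day of the preceding week just prior to treatment". Section 17.0 checks from the diary that the subject's "mean pain intensity score meets the inclusion criteria", which is the only pre-treatment mean the plan describes. The study schedule table has a separate row, "Day 1 (baseline = start of treatment", for a single rating.

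**Rating times.** Section 9.3 takes ratings "At 5- and 10-minutes", and Section 9.4 continues from 1 to 72 hours without a 3-hour or 6-hour rating. The schedule of events adds 6 hours and the table adds 3 hours.

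**The concern.** The trial randomizes ten sham subjects, who give ratings on the same schedule, yet its one stated success criterion does not use them. A single qualifying episode at any time over 48 hours can arise from natural fluctuation, regression toward the subject's usual level, or response to a procedure. Section 8.0 matches sham closely to active treatment ("the sham TCMS device will remain on the area of pain for 10 minutes", with the same sounds at the same intervals), so sham is the natural gauge of how often that happens. A report of 3 or more responders among ten active subjects cannot be interpreted without it.

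The undefined baseline adds a smaller problem. Two analysts could take different references and obtain different counts from the same data. If the diary mean is the reference, the text does not clearly require pain to fall from its level just before the device is switched on.

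**Working it through.** **1. The plan's own figure.** No formula, null responder rate, error rate or variability figure supports either 3 of 10 or the total of 20. Beyond 10 + 10 = 20 there is nothing to reproduce.

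**2. The active-only rule with an inert device.** Inputs: n = 10 and threshold 3 (Section 11.0). The responder rate p, shared by both arms, is assumed at 10%, 20% or 30%. Subjects are treated as independent, and no related serious adverse event is assumed.

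P(X ≥ 3) = 1 − [P(0) + P(1) + P(2)], with X binomial(10, p):

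- p = 0.10: 1 − (0.3487 + 0.3874 + 0.1937) = 0.0702
- p = 0.20: 1 − (0.1074 + 0.2684 + 0.3020) = 0.3222
- p = 0.30: 1 − (0.0282 + 0.1211 + 0.2335) = 0.6172

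**3. The baseline gap, by arithmetic.** On the diary reading, a subject with no change after treatment is 30% below baseline if the Day 1 rating is at most 0.70 × diary mean.

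- Diary 7, 7, 7, 7, 7, 8, 8: mean 51/7 = 7.29, threshold 0.70 × 7.29 = 5.10.
- Day 1 rating 5, and 5 at every later rating: reduction 1 − 5/7.29 = 31.4%.
- The subject satisfies inclusion criterion 8 (at least 5 at enrollment, at least 4 over the preceding 7 days).
- Against the Day 1 rating the reduction is 0%, so the example depends on the diary reading.

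**4. How often this matters.** The documents give no variability, so this is an illustrative simulation in which every distributional input is assumed:

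- subject means normal (mean 6, SD 1.3);
- within-subject SD 1 to 2, correlation time 6 to 24 hours;
- rating noise SD 0.5, integer ratings of pain at the time of rating;
- eligibility as diary mean ≥ 4 and Day 1 ≥ 5;
- ratings at 10 minutes and 1, 2, 4, 8, 12, 24 and 48 hours;
- success as two consecutive qualifying ratings.

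Results at zero treatment effect:

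| Quantity | Range |
|---|---|
| Already at the 30% threshold before the device is on | 1.2–4.3% |
| Chance success against the diary mean | 5.6–21.8% |
| P(at least 3 of 10), diary mean only | 1.6–38% |
| Successes removed by also requiring both ratings below Day 1 | 0.4–1.9% |
| Successes only through pairs with neither rating below Day 1 | about 0.3–0.8% |
| Successes unchanged at every rating | at most about 0.002% |
| P(at least 3 of 10), with the Day 1 condition | 1.2–34% |

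The Day 1 condition therefore lowers P(at least 3 of 10) by only 0.3 to 5.2 percentage points. Most chance success is ordinary fluctuation over the window, which only the sham count can put in context. At within-subject SD 0.5, chance success is about 0.8% and P(at least 3 of 10) about 0.01%. If the floor of 5 applied only at consent, which is the less natural reading, the share removed would be 3.4–11.5%.

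**The case against.** The strongest reply is that Section 12 already compares active with sham and calls this a cumulative responder analysis. As ordinarily understood, that would show the proportion of responders in each arm across reduction thresholds, including 30%. A reader might infer from Section 11 that sham responders will never be seen. The documents do not support that. What remains is that Section 12 does not carry over the 1-hour persistence or the any-time-through-48-hours window, and does not tie its result to 3 of 10.

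A reader might also infer that study success could be reached through subjects whose pain never moved. This goes too far. Section 11 says that the reduction "occurs at any time in the period from treatment through 48-hour follow-up", which can be read to exclude one already present before the device. If Day 1 is the baseline, as the table labels it, the zero-change case disappears altogether. On the diary reading it is arithmetically possible but very rare.

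Finally, the trial is preliminary and unpowered by its own account, no decision is attached to study success, and the lay summary interprets results against sham and says further studies are needed. All of that stands, and it limits the weight of the point. It does not remove the need for a reproducible criterion with its control count beside it.

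**Conclusion.** The concern holds, with minor to moderate weight. Study success rests on active subjects alone, and the plan does not commit to showing the sham count under the same rule. The 7.0%, 32.2% and 61.7% figures are exact binomial results, but the shared responder rates behind them are assumptions. They describe how the rule behaves, not how often sham subjects will respond in this trial.

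The undefined baseline is a secondary point. Using the diary mean is a legitimate choice that needs to be stated. The no-improvement route is a gap in wording and contributes little under the assumed variability, provided the floor of 5 is applied on Day 1.

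It would be tempting to conclude that every correction needs only ratings already collected. That is not established for the persistence rule. The NPRS column header in the schedule table suggests that later ratings may cover the interval since the previous one, whereas the simulation treats each rating as pain at that moment.

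**What to change.** 1. **Sham count.** Apply the Section 11 treatment-success rule identically to sham. Report the sham count (x of 10) beside the active count whenever 3 of 10 is reported, and do not read 3 of 10 as evidence of effectiveness without it.
2. **Baseline.** State in Section 11 that the baseline is the 7-day diary mean. Rename the table row as the Day 1 pre-treatment rating. Require the qualifying ratings also to be below that rating.
3. **Persistence and times.** State how relief lasting at least 1 hour is judged from the ratings, consistently with what the table header asks subjects to rate. Use one list of rating times in Section 9.4, the schedule of events and the table.

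**Cost.** Items 1 and 2 are wording changes that use ratings already scheduled in both arms. Item 3 may change how the rating question is put.

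Under the same assumed model, the Day 1 condition costs few responders. With a true constant 30% reduction, responders go from 61.7–72.3% to 61.5–72.1%, and P(at least 3 of 10) stays at 99% or more. With a true 15% reduction, that probability goes from 45–85% to 43–83%. A subject held at the Day 1 level whose pain would otherwise have risen again is not counted.

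With ten per arm the sham count is context, not a test. At zero effect, when active reaches 3, sham is no more than one responder behind in only 8–50% of simulated trials, so a wider gap can easily be chance.
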